**Figure RHBX.6.8. Flow chart of ADA assessment with clinical interpretation of the various result possibilities.**

### 6.13.8.2. Immunogenicity Analyses

Immunogenicity evaluable patients will be identified as TE-ADA positive, TE-ADA negative, or TE-ADA inconclusive, according to the definitions provided in Section 6.13.8.1.2 and further grouped into TE-ADA status groups and time-varying TE-ADA status groups:

#### **TE-ADA Status Groups:**

- TE-ADA status (positive, negative, or inconclusive)
- NAb status (positive, negative, or inconclusive) for TE-ADA positive patients
- TE-ADA titer groups for TE-ADA positive patients:
  - Low Titer: TE-ADA titer value (last observation carried forward [LOCF]) <1:160
  - Moderate Titer: TE-ADA titer value (LOCF)  $\geq$ 1:160 and <1:1,280
  - High Titer: TE-ADA titer value (LOCF)  $\geq$ 1:1,280

#### **Time-Varying TE-ADA Status Groups:**

Individual ADA samples will be ascribed into 3 different dichotomous variables as explained in Table RHBX.6.11. Each variable has possible values of a “greater-TE-ADA status” or a “lesser-TE-ADA status,” in the sense that the level of TE-ADA detected in the greater-TE-ADA category is higher than in the lesser-TE-ADA category.

**Table RHBX.6.11. TE-ADA Status Dichotomous Variables for AE Analysis**

TE-ADA Status Dichotomous Variable	Greater-TE-ADA Status	Lesser-TE-ADA Status
TE-ADA positive	TE-ADA positive	not TE-ADA positive
TE-ADA moderate-to-high	TE-ADA positive with moderate titer or high titer	not TE-ADA positive, or TE-ADA positive with low titer
TE-ADA high status	TE-ADA positive with high titer	not TE-ADA positive, or TE-ADA positive with low or moderate titer

Abbreviations: AE = adverse event; TE-ADA = treatment-emergent anti-drug antibody.

Note: For purpose of this analysis, TE-ADA Inconclusive is taken to be “not TE-ADA positive.”

Note: A TE-ADA low is defined as a TE-ADA positive with a titer value <1:160; a TE-ADA moderate is defined as a TE-ADA positive with a titer value  $\geq$ 1:160 and <1:1,280; and a TE-ADA high is defined as a TE-ADA positive with a titer value  $\geq$ 1:1,280.

For each TE-ADA status dichotomous variable, a time-varying TE-ADA status will be computed. At time  $t$ , the TE-ADA status is taken to be the highest of the TE-ADA values bracketing time  $t$ . More formally, the TE-ADA status at time  $t$  is given by the greater of (a) the TE-ADA status at the most-recent postbaseline measurement prior to  $t$ , and (b) the TE-ADA status at the first TE-ADA postbaseline measurement at or after time  $t$ . In this computation, “greater” is given by the greater-TE-ADA status of Table RHBX.6.11. If there is no value satisfying criterion (a), then the value (b) is used. Similarly, if there is no value (b), then the value (a) is used.

For each TE-ADA status dichotomous variable, patients will be categorized according to whether they were (i) always in lesser-TE-ADA status postbaseline or (ii) at some point postbaseline, were in greater-TE-ADA status.

#### **6.13.8.2.1. Analyses of Characteristics of ADA Immune Response**

The analyses of characteristics of ADA response will be conducted on all immunogenicity evaluable patients within the Safety Population for the first 16-weeks of Blinded Treatment Dosing Period 2 (Week 0 to 16), and for the All Ixekizumab Exposures Safety Population for the entire 52-week Blinded Treatment Dosing Period 2 when patients are on ixekizumab, including open label rescue with ixekizumab of 80 mg Q2W (time period when patients are on placebo will be excluded), according to [Table RHBX.6.10](#).

The overall frequency and percentage (incidence) of patients will be summarized for the TE-ADA status groups and the time-varying TE-ADA status groups. Scheduled visits, unscheduled visits, and repeat measurements will be included.

In addition, the overall frequency and percentage (incidence) of patients will be summarized for the patients who are baseline ADA positive by TE-ADA status groups. For those patients who are TE-ADA positive, a summary of titer values and the proportion of patients who are NAb positive will also be provided.

The time to the development of TE-ADA (TE-ADA positive, low titer, moderate titer, high titer, and NAb positive) will be calculated as follows:

$$\text{Time to development of TE-ADA/NAb (in weeks)} = (\text{Date of development of TE-ADA/NAb} - \text{Date of first injection of study treatment} + 1) / 7.$$

If a patient has not developed TE-ADAs/NAbs, they will be censored at the date of the last immunogenicity assessment.

Descriptive statistics, including 25th percentile, 50th percentile (median), 75th percentile, and corresponding 95% CIs as well as proportion of TE-ADA/NAb positive by endpoint summarized by treatment group, will also be provided if sufficient data is present. A Kaplan-Meier plot of the time to development of treatment-emergent ADA/NAb will be presented by treatment group, also if sufficient data is present.

For each TE-ADA status dichotomous variable (as defined in [Table RHBX.6.11](#)), summaries will be provided of the total postbaseline time in the greater-TE-ADA status for patients who were at some point postbaseline in the greater-TE-ADA status group. Postbaseline time in greater-TE-ADA status for each patient will be aggregated.

A by-patient listing to include treatment, visit, ADA result, TE-ADA result, NAb result, ADA titer value, and ixekizumab concentration, ADA and NAb inconclusive results will also be provided for the individual studies, for patients with any 1 sample of ADA (or NAb) positive or inconclusive.

### **6.13.8.2.2. Analyses of ADA Effects on Efficacy**

Efficacy analyses for Period 2 will be conducted on all evaluable patients within the safety populations n for Blinded Treatment Dosing Period for Groups 1 and 2, separately. Groups 1 and 2 are illustrated in [Table RHBX.6.10](#).

Assessment of Spondyloarthritis International Society 40 and ASDAS <2.1 (for patients with baseline ASDAS  $\geq$ 2.1) at Weeks 16 with NRI will be summarized by the TE-ADA status groups as described in Section [6.13.8.2.1](#) for the Safety Population.

A logistic regression model with treatment group, TE-ADA status group (excluding patients in the TE-ADA inconclusive category for TE-ADA, excluding TE-ADA positive and co-occurring NAb inconclusive subgroups for NAb) and the interaction of treatment group-by-TE-ADA status group included as factors will be used to test the interaction of treatment group -by-TE-ADA status group during Period 2 at Week 16. The p-value associated with the interaction term will be used to assess if the treatment effect is consistent across the TE-ADA status groups. When the interaction term is statistically significant, the association between responder status and treatment depends, in some manner, on the TE-ADA status group. The interaction will be tested at the 10% significance level. Treatment differences will be evaluated within each subgroup using Fisher's exact test regardless of whether the interaction is statistically significant.

Assessment of Spondyloarthritis International Society 40 and ASDAS <2.1 (for patients with baseline ASDAS  $\geq$ 2.1) at Weeks 52 with NRI will be summarized by the TE-ADA status groups as described in Section [6.13.8.2.1](#) for the All Ixekizumab Exposures Safety Population. No statistical testing will be performed.

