
 
• To explore the effect of starting dose (160 mg compared to 80 mg)
 
	
 
• Onset of action and treatment response (ASAS, ASDAS, CRP, BASFI, BASDAI, spinal pain and SF-36 PCS)
 

 
• To evaluate the incidence of anti-ixekizumab antibodies and its relationship to efficacy of ixekizumab
 
	
 
• Efficacy response rates listed below at Weeks 16 and 52 by treatment-emergent anti-drug antibody (TE-ADA) status and by neutralizing anti-drug antibody (NAb) status                         
 
○ Proportion of patients achieving ASAS40
 
 
 

[figure not shown]
Objectives	Endpoints
	
 
○ Proportion of patients achieving ASAS20
 
○ Proportion of patients achieving ASDAS <2.1
 

 
• To measure ixekizumab exposure and assess the relationship between exposure and efficacy and exposure and immunogenicity
 
	
 
• Serum trough concentrations of ixekizumab
 
• Model parameters for the exposure-response relationship between ixekizumab serum trough concentrations and efficacy endpoints (for example, ASAS20, ASAS40) at Week 16 and/or Week 52
 
• Ixekizumab serum trough concentrations associated with anti-drug antibody (ADA) titer
 

Exploratory Objective	

 
• CCI [REDACTED]
 
	
 
• CCI [REDACTED]
 

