**Safety Population:** Safety analyses for Period 2 will be conducted on the Safety Population, defined as all randomized patients who received at least 1 dose of study treatment. For patients who were deemed as inadequate responders by their investigators and were treated with biologic rescue of ixekizumab 80 mg Q2W, only data up to the time of initiation of biologic rescue of ixekizumab 80 mg Q2W will be included in the Period 2 analyses. Patients will be analyzed according to the treatment to which they were assigned at Week 0.

**Inadequate Responder (IR) Population:** Selected safety and efficacy summaries will be provided for the IR Population, defined as inadequate responders (identified by investigators based on clinical judgment) who had initiated biologic rescue of ixekizumab 80 mg Q2W.

**Follow-Up Population:** Safety analyses for Period 3 will be conducted on the Follow-Up Population, defined as all randomized patients who received at least 1 dose of study treatment and have entered the Period 3. Patients will be analyzed according to the treatment they received before entering the Follow-up Period.

[Table RHBX.6.1](#) summarizes the major analysis purposes intended for each analysis population.

[Table RHBX.6.2](#) describes the treatment groups and the comparisons for each study period and analysis population.

Table RHBX.6.1. Major Analysis Purposes Intended for Each Analysis Population

	Intent-to-Treat (ITT) Population	Per-Protocol Set (PPS)	Inadequate Responder (IR) Population	Safety Population	Follow-Up Population
Disposition	x		x		x
Baseline Characteristics a	x		x		
Treatment Compliance			x	x	
Concomitant Medication	x		x b		
Protocol Deviation	x		x b		
Exposure			x b	x	
Efficacy and Health Outcomes Analyses	x	For ASAS40	Selected efficacy b		
Safety Analyses			Categorical safety b	x	x
Subgroup Analyses on Efficacy	x				
Subgroup Analyses on Safety Outcome				x	

Abbreviation: ASAS40 = Assessment of Spondyloarthritis International Society 40.

a Including patient demographics and other baseline characteristics, historical illness, preexisting conditions, prespecified medical history, previous therapy.

b These summaries will focus on the time period during biologic rescue of ixekizumab 80 mg every 2 weeks (Q2W).

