**Table RHBX.6.2. Treatment Groups and Comparisons for Each Study Period and Analysis Population**

Study Period	Analysis Population	Treatment Group	Abbreviation	Comparison
Blinded Treatment Dosing Period (Period 2)	Intent-to-Treat (ITT) Population; Per-Protocol Set (PPS); Safety Population	Placebo Ixezumab 80 mg Q4W Ixezumab 80 mg Q2W Total Ixezumab Total Add the following treatment groups for analyses evaluating the impact of ixekizumab starting dose: Ixezumab 80 mg Q4W / 80 mg Starting Dose Ixezumab 80 mg Q4W / 160 mg Starting Dose Ixezumab 80 mg Q2W / 80 mg Starting Dose Ixezumab 80 mg Q2W / 160 mg Starting Dose Total Ixezumab / 80 mg Starting Dose Total Ixezumab / 160 mg Starting Dose	PBO IXE80Q4W IXE80Q2W Total IXE Total  IXE80Q4W/80S b IXE80Q4W/160S b IXE80Q2W/80S b IXE80Q2W/160S b Total IXE/80S b Total IXE/160S b	IXE80Q4W vs. PBO IXE80Q2W vs. PBO Overall a  IXE80Q4W/80S b vs. IXE80Q4W/160S b IXE80Q2W/80S b vs. IXE80Q2W/160S b Total IXE/80S b vs. Total IXE/160S b
Blinded Treatment Dosing Period (Period 2)	Inadequate Responder (IR) Population	Placebo IR / Ixezumab 80 mg Q2W Ixezumab 80 mg Q4W IR / Ixezumab 80 mg Q2W Ixezumab 80 mg Q2W IR / Ixezumab 80 mg Q2W Total Ixezumab IR / Ixezumab 80 mg Q2W Total IR / Ixezumab 80 mg Q2W	PBO IR/IXE80Q2W IXE80Q4W IR/IXE80Q2W IXE80Q2W IR/IXE80Q2W Total IXE IR/IXE80Q2W Total IR/IXE80Q2W	No Between-Group or Overall Comparisons
Post-Treatment Follow-Up Period (Period 3) c	Follow-Up Population	Placebo Ixezumab 80 mg Q4W Ixezumab 80 mg Q2W d Total Ixezumab Other Biologic e Total	PBO IXE80Q4W IXE80Q2W Total IXE Other e Total	No Between-Group or Overall Comparisons

Abbreviations: IXE80Q2W = ixekizumab 80 mg every 2 weeks; IXE80Q4W = ixekizumab 80 mg every 4 weeks; PBO = placebo; Q2W = every 2 weeks; Q4W = every 4 weeks.

- a Overall comparison will be conducted for demographics, historical illness, medical history, preexisting condition, and previous therapy. The between-group comparisons and the overall comparison will be conducted for concomitant therapy, compliance, disposition, and safety.
- b S = Starting dose, differences between starting dose groups and 95% confidence interval (CI) will be provided.

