**Table RHBX.6.10. Baseline and Postbaseline Definition for Immunogenicity Analyses in Period 2**

[figure not shown]
Analysis Purpose	Analysis Population	Treatment Group	Baseline Definition	Postbaseline Definition
Incidence of TE-ADA during Week 0-16	Safety Population	Group 1: PBO IXE 80mg Q4W IXE 80mg Q2W Total Ixe	Last non-missing observation on, or prior to the date of the first injection of study drug at Week 0 (before drug administration)	Week 0-16
Incidence of TE-ADA during Week 0 -52 while patients on Ixekizumab exposure	All Ixekizumab Exposure Safety Population a	Group 2: IXE 80mg Q2W – Q2W b IXE 80mg Q4W – Q4W c PBO - IXE 80mg Q2W d IXE 80mg Q4W – Q2W e All IXE 80mg Q2W f	Last non-missing observation on, or prior to the date of the first injection of ixekizumab, that is, PBO – ixe 80mg Q2W, baseline is before ixekizumab 80mg Q2W rescue. For other groups, it is Week 0	Time period between the first ixekizumab injection to the last visit. For patients who may take other biologic rescues (e.g. TNFi), the postbaseline period ends prior to the start of other biologic therapy.

Abbreviations: IXE = ixekizumab; PBO = placebo; Q2W = every 2 weeks; Q4W = every 4 weeks; TE-ADA = treatment-emergent anti-drug antibody; TFFi = tumor necrosis factor inhibitor.

- a defined as all patients who received at least one dose of ixekizumab during the study.
- b includes patients with only ixekizumab 80mg Q2W exposure, regardless of whether patients were rescued by ixekzimab 80mg Q2W
- c Includes patients with only ixekizumab 80mg Q4W exposure. Patients who were rescued by ixekizuamb 80mg Q2W are not included.
- d Includes patients who were originally assigned to placebo and were later on rescued by ixekizumab 80mg Q2W.
- e Includes patients who were originally assigned to ixekizumab 80mg Q4W and were later on rescued by Ixekizumab 80mg Q2W.
- f includes groups 1 and 3.

- **baseline ADA positive (preexisting antibody):** ADA detected in a sample collected at baseline.
- **baseline ADA-negative:** ADA is not detected in a sample collected at baseline.
- **treatment-emergent anti-drug antibody (TE-ADA) positive:** a) a patient with a  $\geq 4$ -fold increase over a positive baseline antibody titer (Tier 3); or b) for a negative baseline titer, a patient with an increase from the baseline to a level of  $\geq 1:10$ .

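### The Week 16 test of antibodies against efficacy uses placebo as comparator within TE-ADA strata, so a non-significant interaction says little about whether antibodies reduce ixekizumab's effect

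*SAP*

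**What the plan says.** The objective in SAP section 4 is: "To evaluate the incidence of anti-ixekizumab antibodies and its relationship to efficacy of ixekizumab". Its endpoints are ASAS40, ASAS20 and ASDAS <2.1 response rates at Weeks 16 and 52 by TE-ADA and neutralizing-antibody (NAb) status.

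SAP 6.13.8.2.2 tabulates ASAS40 and ASDAS <2.1 (the latter in patients with baseline ASDAS of at least 2.1) by TE-ADA status. At Week 16 it adds a logistic model with treatment group, TE-ADA status and their interaction, leaving out TE-ADA inconclusive patients. On the interaction it says "The p-value associated with the interaction term will be used to assess if the treatment effect is consistent across the TE-ADA status groups" and "The interaction will be tested at the 10% significance level". It continues: "Treatment differences will be evaluated within each subgroup using Fisher's exact test regardless of whether the interaction is statistically significant". Week 52 is summarised without testing.

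The section does not list the arms in the model, but three places put placebo in it:
- Table RHBX.6.10 defines the Week 0-16 set as "Group 1: PBO IXE 80mg Q4W IXE 80mg Q2W Total Ixe".
- The Safety Population is "defined as all randomized patients who received at least 1 dose of study treatment" (SAP 6.1.1).
- Table RHBX.6.2 gives the Period 2 comparisons for that population as "IXE80Q4W vs. PBO IXE80Q2W vs. PBO".

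Where the SAP wants placebo left out of a model it says so, as in the starting-dose analyses of 6.1.2.1. No such restriction appears here.

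**The concern.** Treatment-emergent antibody to ixekizumab is a post-exposure response. The placebo arm gets placebo injections only, and its earliest ixekizumab is rescue from Week 16 (Protocol 6.1). A placebo patient classed as TE-ADA positive in the Week 0-16 window therefore shows background reactivity or a titer rise over pre-existing antibody. Such patients should be few, and they are not a control group for patients who made antibody to the drug.

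Two planned quantities depend on that cell. The Fisher test in the positive stratum compares ixekizumab patients with those few placebo patients. The interaction needs the same cell to say how the ixekizumab-placebo difference changes with TE-ADA status.

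At stake is the reading of one secondary result. The SAP directs that this p-value be used to judge consistency, and a non-significant value could reach the study report as evidence that antibodies do not matter.

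**Working it through.** **Inputs.** From SAP 5.2: 100 patients per group and Week 16 ASAS40 of 46% (Q2W) and 18% (placebo). From SAP 6.13.8.2.2: interaction level 0.10. Assumptions: Q4W also at 46%, because no Q4W rate is given; 5, 10 or 20 TE-ADA positives per ixekizumab arm; 0, 1 or 3 in placebo. Neither document gives a TE-ADA rate.

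**Step 1: reproduce the plan's figure.** Sum Bin(x; 100, 0.46) × Bin(y; 100, 0.18) over all (x, y) with two-sided Fisher p ≤ 0.05. The result is 98.8%, against approximately 98% stated. The rates are usable. The documents state no power for the antibody test.

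**Step 2: what the interaction tests.** Three arms by two TE-ADA states give 6 cells. The model without interaction has 4 parameters (intercept, two treatment terms, one status term), so the interaction has 6 − 4 = 2 df. If the placebo-positive cell is empty, 5 − 4 = 1 df is left. The remaining contrast is the positive-versus-negative log odds ratio in Q2W minus the same quantity in Q4W. If antibodies abolish the effect equally in both regimens, that contrast is zero.

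**Step 3: rejection rates.** Likelihood-ratio test of the interaction at 0.10, 2,000 simulated trials per entry. Placebo responds at 18% and TE-ADA negative ixekizumab at 46%. TE-ADA positive ixekizumab responds at 18% (full loss) or 46% (no antibody effect).

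| Placebo positives | Ixekizumab positives per arm | Full loss | No antibody effect |
|---|---|---|---|
| 0 | 5 | 15.4% | 15.3% |
| 0 | 10 | 15.5% | 11.9% |
| 0 | 20 | 11.9% | 10.8% |
| 1 | 5 | 17.5% | 12.3% |
| 1 | 10 | 22.2% | 10.1% |
| 1 | 20 | 21.3% | 9.7% |
| 3 | 5 | 21.8% | 13.1% |
| 3 | 10 | 20.2% | 10.7% |
| 3 | 20 | 16.3% | 8.9% |

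Monte Carlo standard error is about √(0.15 × 0.85 / 2000) = 0.8 percentage points. In the sparsest rows the test does not hold its nominal 10%, so part of the apparent rejection is excess type I error. The section does not say which test of the interaction will be used; the likelihood-ratio form is my choice.

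**Step 4: Fisher test in the positive stratum.** With m placebo and n ixekizumab positives (n > m), the smallest attainable two-sided p is 1/C(n+m, m), reached when all of one group and none of the other respond.
- m = 1: 1/6 = 0.167 (n = 5), 1/11 = 0.091 (n = 10), 1/21 = 0.048 (n = 20).
- m = 2: 1/21 = 0.048 (n = 5), 1/66 = 0.015 (n = 10).
- m = 0: there is no comparator and no test.

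**Step 5: the comparison available in the same data.** Fisher power for TE-ADA positive versus negative among 200 ixekizumab patients, 18% versus 46%:

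| Positives of 200 | Level 0.10 | Level 0.05 |
|---|---|---|
| 10 | 45% | 40% |
| 20 | 81% | 66% |
| 40 | 96% | 93% |

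**Step 6: the inconclusive exclusion.** SAP 6.13.8.1.1 and 6.13.8.1.3 define inconclusive by drug in the sample at a level that may mask antibody. Before Week 16 that can occur only in ixekizumab patients. Excluding the class can therefore remove patients from the active arms only, selected by drug level. Table RHBX.6.11 handles the same patients differently for adverse events, counting them as not TE-ADA positive.

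**The case against.** The strongest reply is that the objective does not rest on this p-value. Its endpoints are response rates by TE-ADA and NAb status, and 6.13.8.2.2 tabulates ASAS40 and ASDAS <2.1 by TE-ADA status at Week 16, and at Week 52 for everyone exposed to ixekizumab. SAP 6.12 also allows graphs of efficacy by antibody status and antibody as a covariate in exposure-response modelling, though only as options. A positive-versus-negative contrast within ixekizumab could be drawn from the planned model, although none is specified. The analysis lies outside the multiplicity scheme. The alternative conditions on a post-randomisation variable, and with 10 positives its power is only 45%. All of this stands. It limits the point to the inferential part and makes the consequence modest.

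The SAP's sparse-data provisions do not repair the test. The fallback to Fisher's test in 6.1.2.1 replaces a treatment comparison and cannot test an interaction. The 10% subgroup rule in 6.15.1 is not repeated here and looks at the whole subgroup, not the placebo cell: 40 positives of 300 is 13% and would pass with an empty placebo cell.

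A reader might also infer more than the documents support:
- That no placebo positives means no interaction test. One df remains, for Q2W versus Q4W.
- That non-significance is near certain. Rejection under full loss is 12-22%.
- That the stratum Fisher test can never reach significance. It can with 20 ixekizumab positives against one placebo positive (0.048), Group 1 includes a pooled ixekizumab column, and the SAP sets no level for these tests.
- That placebo positives are assay errors. The TE-ADA definition also covers a fourfold rise over a positive baseline titer.
- That excluding inconclusive patients biases the negative stratum. It could, but no drug-tolerance limit or count is given, and Protocol 8.8.1 describes an assay designed to detect antibody in the presence of drug.

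**Conclusion.** The point holds for the Week 16 interaction test and the within-stratum Fisher tests against placebo. With no placebo positives, the ixekizumab-placebo contrast in the positive stratum is not estimable and the interaction is blind to an antibody effect common to both regimens. With one or three, the interaction rejects in about 16-22% of trials under complete loss of effect and 9-13% under none. A non-significant p-value should not be reported as consistency of effect.

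The figures rest on assumed TE-ADA counts, a common 46% response in both regimens and a likelihood-ratio test. The structural argument in Step 2 needs none of these. That placebo is in the model is inferred from Table RHBX.6.10, the Safety Population definition and Table RHBX.6.2, because the section itself does not name the arms. The descriptive rates still serve the objective in part.

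**What to change.** In SAP 6.13.8.2.2, for the Week 16 inferential analysis:

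1. Restrict the model to the ixekizumab arms. For ASAS40 and ASDAS <2.1, report TE-ADA positive versus negative, pooled with adjustment for regimen and also by regimen, with 95% CIs. Do the same for NAb status.
2. Label the comparison as non-randomised and associational.
3. Drop the within-stratum Fisher tests against placebo, and show placebo TE-ADA descriptively as a background rate.
4. Remove the sentence that reads the interaction p-value as consistency of the treatment effect.
5. Add one sensitivity run counting TE-ADA inconclusive patients as not positive, as Table RHBX.6.11 already does.

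The cost is SAP wording and one changed table, with no new data. The price is a contrast without the protection of randomisation and, if positives are few, a wide interval. That interval would show plainly how little the data can say.
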